Document Title: Study Protocol and Statistical Analysis Plan

Date: 14 May 2025

“Aalana Palana”, a community-based video-facilitated parenting intervention for child development in Telangana, India: Study protocol

Children thrive developmentally when they are surrounded by systems and relationships that consistently provide nurturing care. This care must operate across both proximal environments—such as the family and community-based workers (CBWs)—and distal influences such as supportive social policies, institutional services, and cultural norms (1). A nurturing home environment includes a constellation of factors: sensitivity and responsiveness to a child's health and nutritional needs, regular and developmentally appropriate opportunities for learning, emotionally enriching caregiver interactions, and protection from both environmental and psychosocial adversity (2). These elements are especially vital during the first 1,000 days of life, a critical window when the brain undergoes rapid development and lays the foundation for future cognitive, social, and emotional functioning.

While global progress has been made in reducing developmental risk, evidenced by a decline in the number of children under five at risk of not reaching their developmental potential from 279.1 million to 249.4 million between 2004 and 2010, the burden remains high, particularly in regions such as South Asia. Many of these risks stem from social and structural inequities that limit caregivers' access to knowledge, stimulation resources, and health-promoting environments (1).

Intervention research from LMICs has consistently demonstrated that programs integrating nutrition with responsive caregiving and play activities, particularly those delivered in the early years, yield significantly better developmental and nutritional outcomes than stand-alone nutritional approaches (3). Parenting programs that emphasize emotionally attuned and developmentally supportive interactions between caregivers and children are especially effective in improving child cognition, caregiver knowledge, parenting behaviors, and the quality of parent-child engagement (4). These findings have led to a global consensus around the need to scale up parenting interventions as a key strategy to support child development.

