Building on global evidence and contextual relevance, this protocol outlines a study to implement and evaluate *Aalana Palana*, a culturally adapted, video-facilitated parenting intervention for caregivers of young children in Telangana, India. The intervention is designed to promote responsive caregiving practices and optimal nutrition in the early years of life. *Aalana Palana* will be integrated within the existing framework of the Integrated Child Development Services (ICDS) and delivered by frontline community-based workers, specifically trained Anganwadi Workers (AWWs). By embedding the intervention within routine maternal and child care services and utilizing pre-loaded video content as the primary delivery modality, the program aims to enhance fidelity, reduce provider burden, and improve caregiver engagement. This study will assess the effectiveness of the intervention in improving child developmental outcomes and the home caregiving environment, and will examine its feasibility as a scalable, low-cost solution for low-resource settings.

Methods

Study Setting

The proposed study will be situated in Telangana, the youngest state in India, established in 2014. Telangana presents a unique context for the implementation of early childhood development (ECD) interventions due to both its demographic characteristics and service delivery infrastructure. According to the National Family Health Survey-5 (2019–21) (14), while maternal and child healthcare indicators in the state have shown progress and are generally better than national averages—such as 70.4% of mothers receiving four or more antenatal check-ups, 97% institutional deliveries, and 84.7% full immunization coverage for children aged 12–23 months—there remain significant gaps in child nutrition and early feeding practices. Only 37.1% of children under three months were breastfed within the

first hour of birth, and just 9.2% of children aged 6–23 months received an adequate diet. Alarmingly, the state has seen a deterioration in under-5 anthropometric indicators over recent years, with increased rates of stunting, underweight, and wasting.

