For the purposes of this study, exposure will be defined as having watched any *Aalana Palana* video within the three-month period preceding data collection.

Outcome Measures

Child development outcomes will be measured using three validated tools appropriate for low- and middle-income country (LMIC) settings:

1. **Family Care Indicators (FCI)** (26)– Developed by UNICEF and adapted from the HOME inventory, this caregiver-report tool assesses the quality of the home environment, focusing on caregiving practices that support early child development in children aged 0–5 years. The FCI includes yes/no items covering the availability of and variety in play materials and play-related activities.

2. **Infant and Young Child Feeding (IYCF) Framework** (27)– This tool captures data on key nutrition indicators, particularly breastfeeding and complementary feeding practices for children under two years of age. It follows WHO and UNICEF recommendations and includes 17 operationally defined indicators to assess adequacy in early feeding practices.
3. **Caregiver Reported Early Development Instruments (CREDI)** (28)– Designed to measure developmental progress in children aged 0–36 months, this population-level, caregiver-reported tool assesses four domains: motor, language, cognitive, and socio-emotional development. The long-form, which includes 108 items, will be used. With necessary permissions, the CREDI tool has been translated into Telugu by the Sangath team to ensure cultural and linguistic relevance for the study population.

These tools have been selected for their strong psychometric properties, appropriateness for use in community settings, and feasibility for administration by trained data collectors.

Data collection

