Two different teams were deployed to collect data between July 2023 and January 2024. This was done to minimize assessor bias by ensuring that exposure and outcome data was collected by two separate teams. The first team comprised of two field workers who mapped the study geography, consented eligible participants, and collected data on geolocations, demographic, socio-economic, and exposure to *Aalana Palana*. The list of consented participants identified by the first team was shared with a second team who visited the households three-to-four weeks post consenting. The second team of non-specialist child development assessors collected all outcome data on FCI, CREDI, and IYCF practices. Data on IYCF practices was collected from a subset of children aged >6 months and <2 years at the time of data collection.

Data Analysis

All data will be analyzed using Stata 15 and SPSS 27.

- Descriptive Analysis: Frequencies, means, and standard deviations will be used to summarize participant characteristics, exposure levels, and outcomes. Group differences will be tested using chi-square tests for categorical variables and t-tests for continuous variables.
- Primary Analysis: Linear regression will be used to estimate the association between intervention exposure and CREDI z-scores, adjusting for child age, child sex, maternal education, FCI score, and AWC registration status.
- Secondary Analyses:
 - Logistic regression will assess the association between exposure and binary outcomes for FCI and MAD.
 - Moderation analysis will examine interaction effects of child age, sex, and maternal education on the primary outcome.

- Mediation analysis will be conducted using structural equation modeling (SEM) to assess whether the effect of the intervention on child development is mediated by the quality of the home environment (FCI score).

Sensitivity Analysis: Subgroup analyses will be performed for caregivers registered at AWCs to account for potential confounding due to engagement with AWC services.

Data Management and Confidentiality

Data will be collected digitally on secure tablets using encrypted platforms (e.g., REDCap). Data will be uploaded to a password-protected server accessible only to designated research personnel. Identifiers will be stored separately from de-identified datasets. Regular backups and integrity checks will ensure data security and accuracy.

Ethics Approval and Consent

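### The home-environment aim has no stated adjusted model with the planned FCI score as outcome; its only named analysis is a logistic regression on a binary outcome that the document does not define

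*Combined protocol and SAP*

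**What the plan says.** - **Aim** (last paragraph before Methods): the study will assess the "effectiveness of the intervention in improving child developmental outcomes and the home caregiving environment". The home environment is thus one of two effectiveness targets.
- **Outcome Measures, item 1**: "The FCI includes yes/no items covering the availability of and variety in play materials and play-related activities". No rule for building a score, no range and no cut-off is given.
- **Data Analysis, Secondary Analyses**: "Logistic regression will assess the association between exposure and binary outcomes for FCI and MAD". No cut-off, item list or covariate list follows.
- **Data Analysis, Primary Analysis**: CREDI z-scores are regressed on exposure, "adjusting for child age, child sex, maternal education, FCI score, and AWC registration status". This is the only covariate list in the plan.
- **Data Analysis, mediation**: a structural equation model (SEM) asks whether the effect on child development runs through the FCI score. No covariates are listed.
- **Data Analysis, Descriptive Analysis**: "Group differences will be tested using chi-square tests for categorical variables and t-tests for continuous variables". FCI is not named here.
- **Limitations**: confounding is to be handled by multivariable regression, with no outcome or covariate named.
- **Timing**: under Data collection, "Two different teams were deployed to collect data between July 2023 and January 2024"; the document carries "Date: 14 May 2025".

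**The concern.** Exposure is the caregiver's own report of having watched a video, and the comparison group is a convenience sample from the same catchments. An effectiveness statement about the home environment therefore needs an adjusted comparison of a stated outcome. The plan already uses an FCI score in two places, yet the analysis that addresses this aim uses an undefined binary instead.

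At stake is how much the study can say on its second target. A cut score would discard information, and the result would depend on where the cut falls. Single items would leave open which outcomes count and how many there are. Data collection ended before the document was dated, so whichever of these choices applies would be made with the data already collected.

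**Working it through.** **Step 1. Every analysis that involves, or could involve, FCI.**

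| Analysis | Role of FCI | Covariates stated | Adjusted estimate of exposure on FCI score? |
|---|---|---|---|
| Primary regression | Covariate (score) | Yes, for CREDI | No, FCI is on the right-hand side |
| Logistic regression | Outcome (binary, undefined) | None | No, not the score |
| SEM | Mediator (score) | None | A path is implied, for a different question and with no adjustment stated |
| Descriptive t-tests | Not named; could include the score | None | No, unadjusted |

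The CREDI covariate list cannot be carried over unchanged to an FCI model because it contains the FCI score. Without that term, four covariates remain.

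**Step 2. If the binary is a cut score.** The documents give no score distribution, sample size, alpha or power, so there is no figure of the plan's own to reproduce. Assume a normal score, two-sided alpha of 5%, and 80% power for the analysis of the uncut score. The relative efficiency of a cut at quantile q is φ(z_q)² / [q(1−q)].

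- q = 0.5: 0.637, a loss of 36%
- q = 0.8: 0.490, a loss of 51%
- q = 0.9: 0.342, a loss of 66%

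Power becomes Φ[(0.842 + 1.960)·√efficiency − 1.960], which is 61%, 50% and 37%.

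A sample-size calculation agrees at the median cut. For a difference of 0.2 SD in equal groups, the score needs 2(1.960 + 0.842)²/0.2² = 393 per group. The cut gives proportions of 0.500 and Φ(0.2) = 0.579. The usual two-proportion formula (pooled variance under the null) then needs 620 per group. The ratio 620/393 = 1.58 matches 1/0.637 = 1.57.

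An FCI total built from yes/no items is discrete, so the normal case is only a guide. For a sum S of k independent items, efficiency is corr(S, 1{S ≥ c})². With k = 3, item probability 0.5 and c = 2, the covariance is 1.125 − 0.75 = 0.375. Efficiency is then 0.375²/(0.75 × 0.25) = 0.75, a loss of 25%. Across k = 3 to 16 and item probabilities of 0.3 to 0.7, the loss at the best cut runs from 25% to 36%.

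**Step 3. If single items are modelled instead.** No cut is made, so Step 2 does not apply. Assume m items, each tested at 5%. The chance of at least one false positive is 1 − 0.95^m for independent tests: 14%, 40% and 56% at m = 3, 10 and 16. With test statistics correlated at 0.5 it is 12.5%, 29% and 37%. The document gives neither m nor a correlation.

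**Step 4. Is a linear model tolerable for a bounded score?** A simulation compared two group means with unequal-variance standard errors and no true effect. It assumed n = 200 or 500, with 30% or 50% exposed. Type I error was 4.7% to 5.8% with about 45% of participants at the maximum score, and 4.9% to 5.2% with about 3% there. The simulation took participants as independent. It therefore says nothing about clustering within the 30 catchments, which the standard errors must handle separately.

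**The case against.** The strongest reply is that logistic regression on a binary outcome is a legitimate secondary analysis, and a proportion is easier to read than a score difference. The SEM must estimate a path from exposure to FCI score, and the descriptive t-tests may cover the score. The Limitations section promises multivariable regression. The cited instrument source may supply scoring or indicator definitions. On this view it would be enough to define the binary and list its covariates, and the losses above are textbook results that show nothing specific to this study.

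Much of this stands. The binary analysis is not an error and should be kept. The magnitudes are conditional illustrations. The outcome is undefined in this document, which is not the same as undefinable. What remains is that neither the SEM path nor the t-tests give a stated, adjusted answer to the home-environment question, and the general promise of regression names no outcome. Defining the binary would make the result interpretable, but would still leave the loss from a cut or the reliance on chosen items. The score is already planned, so using it as the outcome costs one model.

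A reader might infer more than the text supports:

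- *That the score will be dichotomised.* The document does not say so. FCI consists of yes/no items, and the plural in the quoted sentence may only span FCI and MAD.
- *That information loss and multiplicity add up.* They belong to different readings and cannot both apply to the same outcome.
- *That the logistic model is unadjusted.* Its covariates are unstated. That is not evidence that there are none.
- *That the binary was chosen after looking at results.* The dates show only that the document follows data collection.

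**Conclusion.** The point holds as a cheap improvement to a secondary analysis. One of two stated effectiveness targets has no stated adjusted model using the planned FCI score as its outcome, and the one analysis named for it rests on a binary outcome that the document leaves undefined.

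The size depends on which reading applies. For a cut score, the loss is about 36% at a median cut of a normal score, more at uneven cuts, and 25% to 36% at the best cut of a sum of independent items. For single items, the cost is an open number and choice of outcomes. Every figure rests on an assumed distribution, item count, alpha and power, because the document gives none of them. The textual finding needs none of these figures. The primary CREDI estimate is unchanged by this gap.

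**What to change.** 1. State how the FCI score is built.
2. Add, as the main analysis for the home-environment aim, one linear regression of FCI score on exposure. Adjust for the child's age and sex, the mother's education and AWC registration, and cluster the standard errors by AWC catchment (30 areas).
3. Name one fixed sensitivity analysis for the bounded score, such as an ordinal model with the same covariates. Do not leave the model form to be chosen from the data.
4. Keep the binary FCI result as supportive. State its cut-off or item list, and use the same four covariates.
5. Add a dated note that the change was made after data collection.

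The cost is a few sentences, one main regression and one sensitivity model. No new data are needed: the score and the four covariates are already named in the primary model, and households were mapped within the catchments. The downside is that a score difference is harder to interpret than a proportion, which the supportive binary result covers.

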To assess the impact of the *Aalana Palana* intervention, we propose a quasi-experimental, non-randomized post-test only design incorporating a convenience-based comparison group. The study will be conducted in the catchment areas of 30 Anganwadi Centres (AWCs), previously identified as implementation sites through partnerships with government and community stakeholders.

Household mapping within these catchment areas will be undertaken to identify eligible participants, specifically caregivers of children under three years of age. All eligible participants who provide informed consent will be included in the study. The intervention (or “exposed”) group will comprise caregivers who report having viewed an *Aalana Palana* video within the three months preceding data collection.

A comparison (unexposed) group will be formed using a convenience sampling approach, including participants from the same catchment areas who have not been exposed to the intervention. Importantly, participation in the study will not be restricted to households registered at an AWC, allowing for the inclusion of a broader range of community members and enhancing the generalizability of findings within the selected geographies.

This design enables the assessment of real-world exposure and its potential effects under naturalistic conditions while acknowledging limitations related to non-random allocation.

Data Collection Tools

For all participants who consent to participate in the proposed study, basic demographic and identifying information will be collected, including GPS coordinates of households; child’s name, sex, and date of birth; names and dates of birth of parents; contact details; address; and maternal education level. Maternal education will be categorized using classifications from the modified Kuppuswamy scale (25), which has been adapted for Indian socio-economic contexts.

Assessment of Exposure to Aalana Palana

Exposure to the *Aalana Palana* intervention will be determined through a structured set of questions developed by the intervention team. These will include:

- (i) Whether the participant has heard of *Aalana Palana* (with follow-up on the source of information);
- (ii) Whether the participant has watched any *Aalana Palana* video in the three months prior to data collection;
- (iii) Whether anyone in the household has any *Aalana Palana* video stored on their mobile device (with follow-up on the source).

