Ethical approval has been granted by the Sangath Institutional Review Board (Ref: RR_2019_58). Written informed consent will be obtained in the local language (Telugu) from all participants. Illiterate participants will consent via witnessed thumbprint. All field staff will be trained in ethical research practices, confidentiality, and participant rights.

Limitations

This quasi-experimental study may be affected by confounding and selection bias due to the absence of randomization. We will address this through multivariable regression, and subgroup analyses. Lack of baseline data and reliance on caregiver recall are additional limitations. However, use of standardized tools and blinded outcome assessors mitigate potential bias.

References

2. Nurturing care framework progress report 2018-2023: reflections and looking forward [Internet]. [cited 2025 May 11]. Available from: <https://www.who.int/publications/i/item/9789240074460>

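### The mediation analysis makes no allowance for reporting error shared by FCI and CREDI, so if exposure is associated with reported FCI, part or all of the indirect effect may be spurious

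*Combined protocol and SAP*

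**What the plan says.** The mediation plan is one sentence in Data Analysis, under Secondary Analyses: "Mediation analysis will be conducted using structural equation modeling (SEM) to assess whether the effect of the intervention on child development is mediated", the mediator being the FCI score. It does not state the estimator, the covariates in each equation, any error covariance, the test of the indirect effect, or a sensitivity analysis specific to mediation.

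Outcome Measures describes the mediator thus: "this caregiver-report tool assesses the quality of the home environment". It describes CREDI thus: "this population-level, caregiver-reported tool assesses four domains". Under Data collection, "The second team of non-specialist child development assessors collected all outcome data on FCI, CREDI, and IYCF practices", and the only contact described for that team is that the list went to "a second team who visited the households three-to-four weeks post consenting".

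Exposure is also self-reported. In Study Design and Participants, the exposed "group will comprise caregivers who report having viewed an" Aalana Palana video in the previous three months. A different team recorded exposure, at the earlier contact.

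Limitations concedes part of this: "Lack of baseline data and reliance on caregiver recall are additional limitations". Against bias in general it offers multivariable regression, subgroup analyses, standardized tools and blinded outcome assessors. The one listed sensitivity analysis is a subgroup of caregivers registered at an AWC.

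**The concern.** A mediation model multiplies two paths: exposure to FCI (a) and FCI to CREDI given exposure (b). If the same person answers both instruments, a tendency to give favourable answers raises both scores. A more advanced child who prompts more play has a similar effect. Either makes FCI and CREDI correlate within exposure groups even if FCI does nothing to development. Unless the model allows for that correlation, it is read as path b.

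The planned safeguards do not reach this error. Using two teams separates exposure data from outcome data but leaves mediator and outcome together. Blinded assessors and standardized tools do not remove error shared by two reports from one household. The AWC-registered subgroup addresses engagement with services. With three observed variables the model is saturated, so fit statistics cannot flag the fault, and without baseline data the order of FCI and CREDI cannot be examined.

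At stake is the study's only planned analysis of whether the programme works through the home environment.

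**Working it through.** **No figure to reproduce.** The documents give no sample size, alpha, effect size or correlation for this analysis. All inputs below are therefore assumptions: two-sided 5% test, equal groups, total n of 200 to 800, both residual SDs equal to 1.

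**Model.** Let X be exposure. FCI = a·X + e1 and CREDI = 0·X + 0·FCI + e2, with corr(e1, e2) = ρ arising only from shared reporting. The true indirect effect is zero.

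**What the unadjusted SEM estimates.**
- Path b tends to ρ.
- The indirect effect tends to a·ρ. With a = 0.3 and ρ = 0.2, this is 0.3 × 0.2 = 0.06 SD.
- The direct effect tends to −a·ρ = −0.06, so the total effect is 0.

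**Check of scale at n = 400.** SE(a) = 2/√400 = 0.10 and SE(b) ≈ √(0.96/400) = 0.049. The delta-method z is a·b/√(a²·SE(b)² + b²·SE(a)²) = 0.06/√(0.09 × 0.0024 + 0.04 × 0.01) = 0.06/0.0248 ≈ 2.4. A false finding is therefore more likely than not in that setting.

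**Simulated false-mediation rates, delta-method test** (ranges show the spread over separate simulation runs):

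| a (SD) | ρ | n = 200 | n = 400 | n = 600 |
|---|---|---|---|---|
| 0.3 | 0.2 | 23–27% | 71–74% | 93% |
| 0.3 | 0.1 | 4–5% | 23–24% | 47–50% |
| 0.1 | 0.2 | 3% | 10% | 17–18% |
| 0 | 0.2 | 1% | 2–3% | 3–4% |

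With ρ = 0 and a = 0.3 the rate is at most about 1.5–2%, so the excess in the first two rows comes from the shared error. The delta-method test is conservative: the joint-significance test gives about 82–83% at n = 400 with a = 0.3 and ρ = 0.2. Even by that test, a = 0 gives at most about 6% for every ρ from 0 to 0.3 and n from 200 to 800.

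**Reporting style that also shifts reported exposure.** Exposure is self-reported, so a need not reflect a real effect. With no true a or b, n = 400, ρ = 0.2 and a latent correlation of 0.2 between reporting style and reported exposure, joint significance declares mediation in 29% of datasets (10% if the latent correlation is 0.1).

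**What fixing ρ does.** Let r be the FCI–CREDI correlation given exposure. If the residual correlation is fixed at ρ*, then b(ρ*) = r − ρ*·√((1 − r²)/(1 − ρ*²)) in residual SD units, which is zero at ρ* = r. With a = 0.3 and r = 0.2:

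| ρ* | 0 | 0.1 | 0.2 | 0.3 | 0.4 |
|---|---|---|---|---|---|
| a·b(ρ*) | 0.060 | 0.030 | 0 | −0.032 | −0.068 |

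In simulation (n = 400, a = 0.3, true ρ = 0.2, Monte Carlo interval), fixing ρ* at 0.2 cuts false mediation from 82% to 4.7%. Fixing it too low, at 0.1, leaves 44%.

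**The case against.** A reader might infer that the analysis will often declare mediation where there is none, or that common-reporter error alone can produce the finding. The documents do not support either. An exposure–FCI association is also needed; without one the rate stays near or below nominal, and at a = 0.1 and ρ = 0.2 it is only about 10% at n = 400. Because n, a and ρ are all absent from the documents, how often this would happen cannot be derived from them. The condition is nevertheless plausible: the programme aims to improve home care, and exposure is self-selected and self-reported.

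A second objection is that the plan asks whether an effect is mediated, which presupposes one, whereas the illustration has a total effect of zero with indirect and direct paths of opposite sign. If a significant positive total effect were also required, false mediation would fall to about 1–3%. That is correct, but the plan states no such requirement. The primary regression itself adjusts for FCI, so its exposure coefficient is the direct path and does not show the total. Where exposure has a true effect of 0.2 SD on CREDI that does not pass through FCI, false mediation is about 38% at n = 400 even with that requirement.

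Third, one informant and one visit are inferences. This stands: they are the natural reading but are not stated. It also stands that the SEM is unspecified rather than wrongly specified, and that Limitations acknowledges caregiver recall and the missing baseline. No analytic remedy for shared error follows from that acknowledgement.

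Finally, the correlation at which the indirect effect reaches zero is simply the partial correlation of FCI and CREDI, and the data cannot identify the true ρ. That limits the sensitivity analysis to showing how much shared error would be enough to explain the result.

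**Conclusion.** The concern holds conditionally. The plan takes mediator and outcome from caregiver report, through the same team and apparently at the same contact, and says nothing about error common to both. If exposure is associated with reported FCI for any reason, the indirect effect is biased upward by roughly a·ρ (0.06 SD at a = 0.3 and ρ = 0.2), and the chance of falsely declaring mediation ranges from a few per cent to over 90% depending on n, a and ρ. If there is no such association, there is no material inflation. These figures assume a linear single-mediator model with observed scores, positive ρ and no true FCI effect; none of the values comes from the documents. This is a secondary analysis in a design openly described as non-randomized and post-test only, so the point is a recommended improvement and does not undermine the study as a whole.

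**What to change.** Keep the SEM and add three rules to Data Analysis.

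1. Put the same confounders (child age, child sex, maternal education, AWC registration) in the FCI and CREDI equations. This handles measured confounding only, not reporting error.
2. Re-estimate the indirect effect with the FCI–CREDI residual correlation fixed at 0, 0.1, 0.2, 0.3 and 0.4. Report it with the total and direct effects and with the correlation at which it reaches zero, and state that the data cannot identify the true correlation.
3. Label the result exploratory. Describe it as consistent with mediation only if the indirect effect persists (for example, its 95% interval stays above zero) at a threshold correlation fixed before analysis, for example 0.2. Otherwise report a shared association of exposure, FCI and CREDI. If the analysis has already begun, say so and give the date on which the threshold was set.

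The documents place data collection between July 2023 and January 2024, so an independent or observed measure can no longer be added to that round; the remedy has to be analytic. The cost is a few extra runs in the software already named and a sentence or two on interpretation. The downside is a weaker mechanistic claim. An indirect effect that survives the threshold would be more credible than the unadjusted one.
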